EMPOWER CAD

NCT 05755711

Study Title: Equity in Modifying Plaque Of WomEn with UndeRtreated Calcified Coronary Artery Disease (EMPOWER CAD)

NCT Number: NCT 05755711

Protocol Number: CP 67712

Protocol Date: 20 July 2023

Revision: B

Study Device: Shockwave Medical Coronary Intravascular Lithotripsy System

Study Sponsor Name and Address: Shockwave Medical, Inc.
[name]
[name]
USA

CONFIDENTIAL

THIS STUDY PROTOCOL CONTAINS CONFIDENTIAL INFORMATION FOR USE BY THE INVESTIGATORS AND THEIR DESIGNATED REPRESENTATIVES. IT SHOULD BE HELD CONFIDENTIAL AND MAINTAINED IN A SECURE LOCATION. IT SHOULD NOT BE COPIED OR MADE AVAILABLE FOR REVIEW BY ANY UNAUTHORIZED PERSON OR FIRM WITHOUT WRITTEN PERMISSION FROM SHOCKWAVE MEDICAL, INC.

1. Study Summary

Study Title	Equity in Modifying Plaque Of WomEn with UndeRtreated Calcified Coronary Artery Disease (EMPOWER CAD)
Study Objective	To generate real-world clinical evidence associated with coronary IVL in a population of female subjects with calcified coronary artery disease.
Study Device(s), commercially available	Shockwave Medical Coronary IVL System
Manufacturer	Shockwave Medical, Inc.
Intended Use	The Shockwave Coronary IVL System is intended to treat calcified stenoses, including calcified stenoses that are anticipated to exhibit resistance to full balloon dilatation or subsequent uniform coronary stent expansion.
Study Design	Post-market, prospective, multi-center, single-arm observational study
Enrollment	Up to 400 subjects at up to 50 global sites in the US, UK and Europe
Subject Population	Female subjects referred for percutaneous coronary intervention (PCI) with coronary IVL and stenting per standard of care.
Study Duration / Follow-Up Period	Subjects will have clinical follow-up prior to discharge from the index procedure and at 30 days, 1, 2 and 3 years. Follow-up will be via telephone contact (or optional clinic visit).
Primary Safety Endpoint	Target lesion failure (TLF) at 30 days defined as a composite of cardiac death, myocardial infarction (per SCAI definition for peri-procedural MI; per 4 th Universal Definition for spontaneous MI beyond discharge) attributable to target vessel (TV-MI), or ischemia-driven target lesion revascularization (ID-TLR).
Primary Effectiveness Endpoint	Procedural Success defined as stent delivery with a residual in-stent stenosis ≤30% in all target lesions (core laboratory assessed) and without in-hospital TLF (CEC adjudicated).

	
informed of the nature of the study, agrees to its provisions, and has provided written informed consent, approved by the appropriate Institutional Review Board (IRB) or Ethics Committee (EC)

Study Exclusion Criteria	
1. Subjects with known mental or physical illness or known history of substance abuse that may cause non-compliance with the protocol, confound the data interpretation, or is associated with a life expectancy of less than one year2. Subjects presenting with cardiogenic shock at the time of the index procedure3. Serious angiographic complication in the target vessel prior to treatment with coronary IVL including severe dissection (Type D to F), perforation, abrupt closure, persistent slow-flow or persistent no reflow4. Subject unable to tolerate anticoagulation/antiplatelet therapy per guidelines5. Subject is enrolled in any study of an investigational device or drug that may interfere with study results
Study Statistical Methods	
• Intent-to-Treat (ITT) analysis with pre-defined subgroups• Designed to assess exact 95% confidence interval (CI) for primary endpoints; no formal hypothesis testing
Study Sponsor/Study Management	
Shockwave Medical, Inc. [name] [name] USA
 
Contact: [name] Title: Director, Clinical Affairs Telephone (direct): [contact] Email: [contact]

[REDACTED]	[REDACTED]

EMPOWER CAD

NCT 05755711

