5.0 Index Procedure

5.1 Coronary Intravascular Lithotripsy Procedure

A full description of the IVL procedure is detailed in the Instructions for Use (IFU) including appropriate balloon sizing. Note that there are specific IFUs and labelling provided for the United States (US) and for Outside of the US (OUS). An appropriately-sized IVL catheter should be selected per the IFU.

The recommended procedural steps outlined below represent an “IVL first” approach; adjunctive devices may be used if there are challenges after first attempting to cross with the IVL catheter [REDACTED]

[REDACTED] Any departures from this algorithm will not be considered protocol deviations; information on all devices used in the procedure (including the order in which they were used) will be captured. Angiographic images captured during the procedure will be sent to the core lab for analysis.

- If multiple lesions are to be treated, it is recommended that non-target lesions be preferentially treated first.
- If a serious angiographic complication occurs in a target or non-target vessel prior to insertion of the IVL catheter, the subject should be treated per standard of care; however, they should not be enrolled in the study.
- If the Investigator is able to pass a guidewire but is unable to pass the IVL catheter across the target lesion, an adjunctive tool (balloon, atherectomy, cutting/scoring balloon) may be used prior to re-insertion of the IVL Catheter. The lesion will then be treated per the IFU with the IVL Catheter.

Note: Pre-dilatation may be performed using standard techniques based on physician discretion.

- The subject is considered enrolled once the IVL Catheter has been inserted into the access artery.
- Once the IVL catheter is placed in the target lesion area, the balloon should be inflated to 4 atm and IVL treatment delivered for the pre-programmed time of 10 seconds to deliver 10 pulses.

Note: The IVL Generator is programmed to force a minimum pause time of 10 seconds following every 10 pulses delivered.

- Following IVL, inflate the balloon to the reference size using the balloon compliance chart (refer to IFU) and record lesion response on fluoroscopy.
- Deflate the balloon to re-establish blood flow.
- Repeat prior steps for additional treatment cycles until the lesion has been sufficiently dilated or the catheter is re-positioned.

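### Do exclusion criterion 3 and section 5.1 set conflicting entry rules, so that a subject could be dropped because of an outcome?

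*Combined protocol and SAP*

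**What the plan says.** The Study Summary lists as exclusion criterion 3 a "Serious angiographic complication in the target vessel prior to treatment with coronary IVL including severe dissection", and goes on to perforation, abrupt closure and persistent flow disturbance. It concerns the target vessel, and its time limit is treatment with IVL.

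Section 5.1 has its own rule. It begins "If a serious angiographic complication occurs in a target or non-target vessel prior to insertion of the IVL catheter", and says that such a subject gets standard care and does not enter the study. It then fixes the moment of entry: "The subject is considered enrolled once the IVL Catheter has been inserted into the access artery".

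The same section treats insertion and treatment as separate events. On delivery it says: "Once the IVL catheter is placed in the target lesion area, the balloon should be inflated to 4 atm and IVL treatment delivered". If the catheter will not cross the lesion, "an adjunctive tool (balloon, atherectomy, cutting/scoring balloon) may be used prior to re-insertion of the IVL Catheter", after which "The lesion will then be treated per the IFU with the IVL Catheter".

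Section 3.4 makes the Intent-to-Treat (ITT) cohort, meaning everyone enrolled, the primary analysis population. The Study Summary also names ITT as the analysis approach. The events in criterion 3 reappear among the secondary endpoints as serious angiographic complications, and their absence is required for both versions of Angiographic Success.

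**The concern.** The two rules differ in vessel and in time limit. The time limit is the part that looks harmful. Enrolment happens when the catheter enters the access artery, whereas criterion 3 runs until IVL is delivered. Between the two lies an interval that the recommended sequence itself provides for, since "adjunctive devices may be used if there are challenges after first attempting to cross with the IVL catheter". If the catheter never crosses, that interval does not close at all.

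A severe dissection or perforation of the target vessel in this interval happens to a subject who is already enrolled, yet who fits the words of criterion 3. If a site or an analyst then called her ineligible and removed her, she would leave the data because of an outcome. The complication rate would fall and Angiographic Success would rise. In a single-arm study no comparison group would show that this had happened.

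**Working it through.** The plan states no figure on this point, so the check sets the rules side by side for each place and time at which a complication can occur.

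| Complication occurs | Criterion 3, read literally | Section 5.1 | Population under section 3.4 |
|---|---|---|---|
| Before catheter insertion, target vessel | Excluded | Not enrolled | Outside ITT |
| Before catheter insertion, other vessel | Silent | Not enrolled | Outside ITT |
| After insertion, before IVL delivery, target vessel | Wording is met | Already enrolled | In ITT |
| After insertion, before IVL delivery, other vessel | Silent | Already enrolled | In ITT |
| After IVL delivery | Does not apply | Already enrolled | In ITT |

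1. **Vessel scope.** The second row is where this difference affects entry. Criterion 3 does not require such a subject to be enrolled; it only fails to exclude her. Section 5.1 adds a wider bar, and a site that applies it complies with both texts.

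2. **Time limit.** Only the third row has a clash. Section 5.1 states when a complication prevents entry and when entry takes place, and the two moments coincide. Section 3.4 then classifies the subject by whether she was enrolled. No visible passage takes an enrolled subject out of ITT for meeting an exclusion criterion, and the visible text defines no per-protocol set. She stays in, and her complication counts as an outcome.

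3. **Missing-data rules.** Sections 3.1 and 3.5 do not offer a way to drop her. Her complication is observed data, and section 3.5 says that available data are presented.

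4. **Effect if section 3.4 were ignored.** Let n subjects include x with a serious complication, and remove k of those x (k < n). The change in the rate is

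   x/n − (x − k)/(n − k) = k(n − x) / [n(n − k)].

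   Since x is at least k, this is at most k/n. With n = 400 (section 3.3) and k = 1, the bound is 1/400 = 0.25 percentage points. For Angiographic Success with s successes, removing k failures changes the rate by s/(n − k) − s/n = sk/[n(n − k)]. Since s is at most n − k, the bound is again k/n. Both changes are favourable to the device.

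5. **Likely number.** The documents give no frequency for a failed crossing, for use of another device after it, or for complications in that interval. The value of k cannot be estimated, and none is assumed here beyond the per-subject bound.

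6. **Primary endpoints.** Serious angiographic complications are not a component of 30-day target lesion failure or of Procedural Success. A primary result would move only if the removed subject had also failed that endpoint.

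**The case for a change.** The strongest case for acting is that the ITT rule governs the analysis, while eligibility is applied by up to 50 sites. A site working from the summary list could cite criterion 3 to declare an enrolled subject ineligible. It could also miss the wider vessel scope in section 5.1. Section 1.1 associates atherectomy, one of the tools allowed in the interval, with more dissections and perforations, so the event is plausible. Section 3.3 says that the point estimates may serve as a reference for later studies. The correction would be a few words.

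Some of this stands. The two texts do differ, the interval is real, and any wrongful removal would act in one direction only. The rest does not carry through to the results. Exclusion criteria ordinarily govern entry, and section 5.1 applies this one in that way. Calling a subject ineligible after enrolment does not un-enrol her, and section 3.4 looks only at enrolment. The background on atherectomy gives no rate for this interval, and failed crossing is a contingency in the sequence. The remark about reference use sits in a sample-size section built on Procedural Success, which does not contain these complications.

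Section 5.1 also says "Any departures from this algorithm will not be considered protocol deviations". The visible context is the order of devices, and text next to it is redacted, so nothing can be drawn from it about the enrolment bar. Section 4 is absent from the public text and could hold further eligibility rules; that counts neither way.

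**Conclusion.** No change to the plan follows. This is an inconsistency in eligibility wording, and aligning the two texts would be harmless tidying that alters no reported result. With the plan applied as written, the effect on the primary endpoints, the serious-complication rate and Angiographic Success is zero, because section 3.4 keeps the affected subject and counts her complication. The bias needs someone to depart from section 3.4, and it would then be at most 0.25 percentage points per subject removed out of 400.

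This rests on two assumptions: that ITT is applied as section 3.4 defines it, and that no unpublished text removes enrolled subjects after the fact. Nothing here says which vessel scope is right; that choice belongs to the sponsor.

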1.0 INTRODUCTION/BACKGROUND

1.1 Calcified Coronary Lesions

Coronary artery calcification (CAC) is common especially in the elderly population and those with more advanced disease. Approximately 38% and 73% of all lesions display calcification as detected by angiography and intravascular ultrasound (IVUS), respectively [1]. As IVUS is not routinely used as a diagnostic modality, coronary calcification is most likely underestimated [2].

Conventional percutaneous coronary intervention (PCI) to treat calcified lesions has a greater risk of stent underexpansion and malapposition, both of which are associated with adverse clinical outcomes [3]. To facilitate stent placement and optimize stent expansion in calcified lesions, adjunctive plaque-modifying devices are often used including atherectomy (rotational, orbital, laser) and cutting/scoring balloons [4]. Despite advances in interventional equipment and techniques, effective treatment for patients with advanced coronary calcification remains a challenge. Compared to non-calcified lesions, calcified coronary lesions are associated with a higher incidence of major adverse cardiac events (MACE), especially, the rate of non-Q-wave myocardial infarction (MI) [5]. Calcified lesions are associated with a high frequency of restenosis, target lesion revascularization (TLR), vessel dissection during PCI, failure to deliver a stent, balloon ruptures and undilatable lesions [2]. In a study of pooled data from 6,855 patients, the presence of calcification was associated with an increase in the rate of ischemic events at 1 year, especially within the first 30 days, reflecting the negative impact of calcification during stent implantation resulting in an increase in acute and subacute stent failure [6].

Women with moderate-to-severe lesion calcium are particularly vulnerable to poor outcomes. In a dedicated DES registry of 6371 female patients, of which 1622 (25.5%) had moderate/severe calcium, outcomes at 3 years were significantly worse with a reported 38% higher mortality, a 48% higher rate of death or myocardial infarction (MI), and a 56% higher rate of death, MI, or target lesion revascularization (TLR) compared with treatment of mildly or noncalcified lesions [7]. Plaque modification with atherectomy improves lesion compliance, allowing optimal stent expansion, but is associated with increased periprocedural complications including coronary dissections, perforation, and higher rates of periprocedural MI [2, 8, 9]. The procedural risks of atherectomy are accentuated in women who have rates of serious flow-limiting coronary dissections and cardiac tamponade that are 4- to 5-fold higher than men treated with rotational atherectomy, leading to 2-fold higher rates of in-hospital major adverse cardiac events (MACE) [10]. Similar results have been reported with orbital atherectomy [11]. Acute procedural complications in women may limit the use of atherectomy to optimize DES expansion (one of the strongest predictors of subsequent stent thrombosis and restenosis) [12, 13] and likely contribute to the poor outcomes reported in the longer term.

1.2 Coronary Intravascular Lithotripsy

Lithotripsy is a technology originally designed to fragment renal calcifications by pulsing them with high-power acoustic shock waves [14]. The design concept of the Shockwave Coronary IVL System is to use the same core lithotripsy technology, albeit at energy levels that are orders of magnitude lower in intensity and number [15]. The Shockwave Coronary IVL catheter is based on conventional balloon catheter concepts; however, the balloon is inflated at a lower than nominal pressure and the lithotripsy emitters are energized thereby generating pulsatile mechanical energy within the balloon at the target treatment site, disrupting calcium within the

 SHOCKWAVE <small>MEDICAL INC</small>	EMPOWER CAD NCT 05755711
--	---

lesion, and allowing subsequent dilatation of coronary artery stenosis using low balloon pressure.

The Shockwave Coronary IVL System has been evaluated as an adjunct to coronary stenting in severely calcified lesions in the four Disrupt CAD studies: Disrupt CAD I-IV [16-19]. These individual single-arm, prospective, multicenter, nonrandomized studies demonstrated high rates of device and procedural success as well as excellent early angiographic and clinical outcomes, providing evidence for device performance and safety as well as insights into the mechanism(s) of calcium modification.

A patient-level pooled analysis was completed for the Disrupt CAD I-IV studies which showed the very low rates of serious angiographic complications in the pooled analysis are consistent with the IVL mechanism of action which involves circumferential and longitudinal multiplane calcium fracture in situ without the generation of atheroembolic debris and/or significant heat energy [20]. In severely calcified lesions, IVL improves vessel compliance, mitigating the need for aggressive high-pressure balloon dilatation prior to stent delivery, with its associated potential for barotrauma and severe dissection. This unique mechanism of action is reflected by the significant improvements observed by quantitative coronary angiography in minimal luminal diameter (MLD) and percentage diameter stenosis after IVL alone despite an average peak IVL balloon pressure of only 6 atm [15].

An additional analysis was performed on the patient-level pooled data from the Disrupt CAD I-IV studies to evaluate sex-based outcomes of severely calcified coronary lesions treated with IVL lesion preparation before stent implantation [21]. Results showed that IVL-facilitated DES implantation was safe and effective independent of patient sex and was associated with infrequent angiographic complications, without evidence of excess acute angiographic or clinical complications in women [21].

1.3 Study Rationale

The pooled Disrupt CAD I-IV analysis represents the largest series evaluating sex-based outcomes with coronary IVL and included data from 144 women. The EMPOWER CAD study is designed to expand upon this clinical foundation by prospectively enrolling up to 400 female patients and addressing some of the limitations of the pooled analysis [21]. Specifically, EMPOWER CAD is an all-comers study which will enroll a broader population including patients with acute coronary syndromes and those with more complex lesions that were excluded from the CAD I-IV studies including ostial, unprotected left main, length >40 mm, and those lesions with moderate calcium. The EMPOWER CAD study will also provide longer-term outcomes up to three years. Lastly, by generating real-world clinical evidence associated with coronary IVL in a population of female patients with calcified coronary artery disease, the EMPOWER CAD study aims to directly address the underrepresentation of women in cardiovascular clinical trials [22].

2.0 Study Device Description

2.1 Shockwave Coronary IVL System

The commercially available Shockwave Coronary IVL System consists of an IVL Catheter that is used exclusively with the IVL Generator, IVL Connector Cable and its accessories. The IVL Connector Cable is a remote actuator which connects the IVL Generator to the IVL Catheter and is used to activate the lithotripsy therapy from the IVL Generator, refer to Figure 1. Representative Shockwave IVL System.

Figure 1. Representative Shockwave IVL System

2.4 Indications for Use

The Shockwave Coronary IVL System (study devices) utilized during the conduct of this study will be commercially available. Refer to the associated IFUs for each country's approved device indication.

3.0 STATISTICAL CONSIDERATIONS

3.1 General Statistical Methods

Descriptive statistics will be provided in this clinical study. Analyses will be conducted at pre-specified time points including 30 days, 1, 2 and 3 years.

Categorical variables will be summarized by the number of observations available, frequency, and percentage. Unless otherwise noted, missing data will be excluded from the denominator. Comparisons will utilize a Chi-square test, or Fisher's exact test when 20% or more of expected cell frequencies are less than 5. Clinical outcomes analyzed at 30 days will be evaluated as categorical (binary) data. McNemar's chi-square may be used to assess within-subject changes in a bivariate response variable. Exact confidence intervals will be generated for estimates of proportions.

Continuous variables will be summarized by the mean, standard deviation, median, minimum, and maximum. Within-subject changes will be analyzed parametrically using the Paired t-test if the differences are normally distributed, or non-parametrically using the Sign-Rank Test if the differences are not normally distributed. Asymptotic confidence intervals will be generated for estimates of means.

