3.2.2 Primary Effectiveness Endpoint

The primary effectiveness endpoint is Procedural Success defined as stent delivery with a residual in-stent stenosis $\leq 30\%$ in all target lesions (core laboratory assessed) and without in-hospital TLF (CEC adjudicated).

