3.3 Sample Size Determination

The sample size was calculated based on the precision of the exact 2-sided 95% confidence interval (CI) of the primary effectiveness endpoint, using Disrupt CAD III female subgroup results as a reference [18].

 SHOCKWAVE MEDICAL INC	EMPOWER CAD NCT 05755711
---	-----------------------------

The calculation of the EMPOWER CAD sample size was based on a procedural success estimate of 90.0%. Combined with a desired precision of +/- 3.1% and an alpha of 0.05 (95% CI), a sample size of 360 was selected to provide a probability width (“power”) of 0.8. Assuming a lost-to-follow-up rate of 10%, up to 400 subjects will be enrolled.

The EMPOWER CAD study will enroll a broader population relative to the prior pooled analysis from CAD I-IV; as such, point estimates from this real-world population may be used as reference for future studies.

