3.4 Population Analysis

The primary analysis population will be the Intent-to-Treat (ITT) cohort which includes all enrolled subjects.

[figure not shown]

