3.5 Handling of Dropout of Missing Data

No imputation of or adjustments for missing data will be performed for the primary analyses. All available data will be presented. For time to event analyses, subjects who do not experience the event in question will be censored at their last known follow-up.

EMPOWER CAD

NCT 05755711

EMPOWER CAD

NCT 05755711

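### Does an available-case denominator undermine the all-enrolled Procedural Success rate?

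*Combined protocol and SAP*

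**What the plan says.** Section 3.4 defines the primary population as the "Intent-to-Treat (ITT) cohort which includes all enrolled subjects". Section 5.1 fixes the moment of enrolment: "The subject is considered enrolled once the IVL Catheter has been inserted into the access artery". That is before stenting and before the final angiogram.

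Section 3.1 sets the rule for categorical variables: "Unless otherwise noted, missing data will be excluded from the denominator". The sentence just before it says that these variables are reported with the number of available observations as well as the frequency and percentage. Section 3.5 adds "No imputation of or adjustments for missing data will be performed for the primary analyses" and says that all available data will be shown.

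Under section 3.2.2 a success needs three things: a delivered stent, a core-laboratory residual in-stent stenosis of at most 30% in every target lesion, and no in-hospital TLF as adjudicated by the CEC. For the stenosis reading, section 5.1 says "Angiographic images captured during the procedure will be sent to the core lab for analysis" and provides for a final angiogram after stenting and post-dilatation, specifically to assess this endpoint.

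The Study Summary describes the inferential aim: "Designed to assess exact 95% confidence interval (CI) for primary endpoints; no formal hypothesis testing".

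**The concern.** An intent-to-treat label suggests a denominator of everyone enrolled. The missing-data rule gives a smaller one: a subject with no known failed component, but with one unreadable target lesion or an in-hospital TLF status that cannot be adjudicated, drops out of the rate.

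If such subjects did worse than the rest, the reported success rate would be too high. The exact CI would not show this, because it covers sampling error only. With no hypothesis test, the estimate and its interval are the study's result, and section 3.3 says that "point estimates from this real-world population may be used as reference for future studies". A shift carried into a later study's benchmark would matter. The readable text describes no sensitivity analysis that would show its possible size.

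**Working it through.** **Inputs.** From section 3.3: assumed success 90.0%, precision ±3.1 points, two-sided 95% interval, 360 subjects, 10% lost to follow-up, up to 400 enrolled. The number *m* of unclassifiable subjects is not in the documents, so it is varied here as an assumption.

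**The plan's own figures.** Normal approximation: 1.96² × 0.9 × 0.1 / 0.031² ≈ 360, and 360 / 0.9 = 400. Both reproduce. (The exact half-width at 324/360 is 3.24 points, slightly wider than 3.1. That is a separate matter and does not affect this point.)

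**Who can drop out.** Set section 3.2.2 beside section 3.1:
- No stent delivered: known failure, stays in the denominator.
- Any target lesion read above 30%: known failure, stays in.
- In-hospital TLF: known failure, stays in, even if a film is unreadable.
- No known failed component, but a reading or an adjudication is missing: excluded.

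Only the last group matters. Loss to follow-up after discharge cannot create it, because every component is fixed by discharge. The 10% allowance in section 3.3 is therefore no forecast of *m*.

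**Bounds.** Let *x* be the whole number of successes nearest 90% of (400 − *m*). Reported rate = *x*/(400 − *m*), worst case = *x*/400, best case = (*x* + *m*)/400. Intervals are Clopper-Pearson 95%.

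| *m* | Reported | Exact 95% CI | Worst case | Best case |
|---|---|---|---|---|
| 4 (1%) | 356/396 = 89.90% | 86.50–92.69 | 89.00% | 90.00% |
| 8 (2%) | 353/392 = 90.05% | 86.65–92.83 | 88.25% | 90.25% |
| 15 (3.75%) | 346/385 = 89.87% | 86.41–92.70 | 86.50% | 90.25% |
| 16 (4%) | 346/384 = 90.10% | 86.67–92.90 | 86.50% | 90.50% |
| 20 (5%) | 342/380 = 90.00% | 86.53–92.83 | 85.50% | 90.50% |

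The worst case is still inside the reported interval at 15 and first falls outside at 16. The crossing point is 19 if the observed rate is 85% (324/381, lower limit 81.06% against 81.00%) and 12 if it is 95% (369/388, lower limit 92.46% against 92.25%).

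**Less extreme cases.** The all-enrolled rate differs from the reported rate by (*m*/400) × (reported success − success among the unclassified). If the unclassified succeed as often as the others, the difference is zero. If half of them fail, five times the planned 10% failure rate:
- *m* = 20: 0.05 × (0.90 − 0.50) = 2.0 points, giving 88.0%, inside 86.53–92.83.
- *m* = 30: 0.075 × (0.90 − 0.50) = 3.0 points, giving 87.0%, inside the interval for 333/370 (86.48–92.86).

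**What the planned tables already show.** Section 3.1 gives the number with data and the number of successes. With the number enrolled, these yield *m*, both bounds and their exact intervals. A bounds table would use no further data.

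**The case for a change.** The strongest case for acting is that the study's output is an estimate meant to be reused, that a reader may take the intent-to-treat label to mean an all-enrolled denominator, and that stating the bounds in advance costs a sentence or two and two table rows. The best-to-worst span equals the unclassifiable share, so it exceeds the 3.1-point precision target once more than 12 of 400 subjects are unclassifiable (13/400 = 3.25%). At the full 10% allowance it would run from 324/400 = 81.0% to 364/400 = 91.0%.

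The arithmetic stands, and printing the bounds would be reasonable practice. Three things weaken it as a criticism of the plan:
- The 10% case borrows an allowance for follow-up loss, which does not apply to an endpoint settled by discharge.
- A rule that a known failed component counts as failure would only repeat section 3.2.2.
- The absence cannot be confirmed. A figure in section 3.4 is not shown, section 4.0 is not readable, and neither the pre-defined subgroups named in the Study Summary nor the time-to-event analyses mentioned in section 3.5 are described in what can be read. Section 3.1 allows for exceptions noted elsewhere, and section 3.5 bars imputation only in the primary analyses. A supplementary analysis may exist in the missing text.

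**Conclusion.** The concern does not hold. Followed as written, the plan gives a disclosed available-case estimate with its denominator reported. Sections 3.1, 3.4 and 3.5 are consistent, known failures stay in the rate, and no pass/fail decision depends on the result.

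The possible shift is at most 1.8 points in the worst case at 2% unclassifiable (90.05% − 88.25%). It exceeds the reported sampling uncertainty only from about 16 of 400 subjects, all of them failures despite having no known failed component. This rests on 400 enrolled, about 90% observed success, and an assumed number unclassifiable; with observed success between 85% and 95% the threshold is 19 to 12 subjects. If the study report showed considerably more unclassifiable subjects than that, the bounds would deserve attention, and the reported counts would allow them to be calculated then.
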